 G34y000 Chronic coronary insufficiency
 G1yz100 Rheumatic left ventricular failure
 SP11111 Heart failure as a complication of care
 SP11200 Cardiorespiratory failure as a complication of care
 SP11100 Cardiac insufficiency as a complication of care
 P6yy200 Congenital cardiomegaly
 Q48y100 Congenital cardiac failure
 Q490.00 Neonatal cardiac failure
 14A6.00 H/O: heart failure
 14AM.00 H/O: Heart failure in last year

Peripheral Vascular Disease

RG73..00 Other peripheral vascular disease
 RG73..11 Peripheral ischaemic vascular disease
 RG73..12 Ischaemia of legs

RG73..13	Peripheral ischaemia
RG731.00	Thromboangiitis obliterans
RG731000	Buerger's disease
RG731100	Presenile gangrene
RG731z00	Thromboangiitis obliterans NOS
RG73y.00	Other specified peripheral vascular disease
RG73y000	Diabetic peripheral angiopathy
RG73y100	Peripheral angiopathic disease EC NOS
RG73y200	Acrocyanosis
RG73y400	Acroparaesthesia - Schultze's type
RG73y600	Acroparaesthesia - unspecified
RG73y700	Erythrocyanosis
RG73y800	Erythromelalgia
RG73y811	Erythralgia
RG73yz00	Other specified peripheral vascular disease NOS
RG73z.00	Peripheral vascular disease NOS
RG73z000	Intermittent claudication
RG73z011	Claudication
RG73z100	Spasm of peripheral artery
RG73zz00	Peripheral vascular disease NOS

Transient Ischemic Attack / Stroke

G63..00	Precerebral arterial occlusion
G63..11	Infarction - precerebral
G63..12	Stenosis of precerebral arteries
G630.00	Basilar artery occlusion
G631.00	Carotid artery occlusion
G631.11	Stenosis, carotid artery
G631.12	Thrombosis, carotid artery
G632.00	Vertebral artery occlusion
G634.00	Carotid artery stenosis
G63y.00	Other precerebral artery occlusion
G63y000	Cerebral infarct due to thrombosis of precerebral arteries
G63y100	Cerebral infarction due to embolism of precerebral arteries
G63z.00	Precerebral artery occlusion NOS
G64..00	Cerebral arterial occlusion
G64..11	CVA - cerebral artery occlusion
G64..12	Infarction - cerebral
G64..13	Stroke due to cerebral arterial occlusion
G640.00	Cerebral thrombosis
G640000	Cerebral infarction due to thrombosis of cerebral arteries
G641.00	Cerebral embolism
G641.11	Cerebral embolus
G641000	Cerebral infarction due to embolism of cerebral arteries
G64z.00	Cerebral infarction NOS
G64z.11	Brainstem infarction NOS
G64z.12	Cerebellar infarction
G64z000	Brainstem infarction
G64z100	Wallenberg syndrome
G64z111	Lateral medullary syndrome

G64z200	Left sided cerebral infarction
G64z300	Right sided cerebral infarction
G64z400	Infarction of basal ganglia
G65..00	Transient cerebral ischaemia
G65..11	Drop attack
G65..12	Transient ischaemic attack
G65..13	Vertebro-basilar insufficiency
G650.00	Basilar artery syndrome
G650.11	Insufficiency - basilar artery
G651.00	Vertebral artery syndrome
G651000	Vertebro-basilar artery syndrome
G652.00	Subclavian steal syndrome
G653.00	Carotid artery syndrome hemispheric
G654.00	Multiple and bilateral precerebral artery syndromes
G655.00	Transient global amnesia
G656.00	Vertebrobasilar insufficiency
G65y.00	Other transient cerebral ischaemia
G65z.00	Transient cerebral ischaemia NOS
G65z000	Impending cerebral ischaemia
G65z100	Intermittent cerebral ischaemia
G65zz00	Transient cerebral ischaemia NOS
G66..00	Stroke and cerebrovascular accident unspecified
G66..11	CVA unspecified
G66..12	Stroke unspecified
G66..13	CVA - Cerebrovascular accident unspecified
G660.00	Middle cerebral artery syndrome
G661.00	Anterior cerebral artery syndrome
G662.00	Posterior cerebral artery syndrome
G663.00	Brain stem stroke syndrome
G664.00	Cerebellar stroke syndrome
G665.00	Pure motor lacunar syndrome
G666.00	Pure sensory lacunar syndrome
G667.00	Left sided CVA
G668.00	Right sided CVA
G669.00	Cerebral palsy, not congenital or infantile, acute
G680.00	Sequelae of subarachnoid haemorrhage
G681.00	Sequelae of intracerebral haemorrhage
G682.00	Sequelae of other nontraumatic intracranial haemorrhage
G683.00	Sequelae of cerebral infarction
G68W.00	Sequelae/other + unspecified cerebrovascular diseases
G68X.00	Sequelae of stroke,not specfd as h'morrhage or infarction
G6W..00	Cereb infarct due unsp occlus/stenos precerebr arteries
G6X..00	Cerebrl infarctn due/unspcf occlusn or sten/cerebrl artrts

Chronic Liver Disease

A707.00	CHRONIC VIRAL HEPATITIS
A707000	CHRONIC VIRAL HEPATITIS B WITH DELTA-AGENT
A707100	CHRONIC VIRAL HEPATITIS B WITHOUT DELTA-AGENT
A707200	CHRONIC VIRAL HEPATITIS C

A707X00 CHRONIC VIRAL HEPATITIS, UNSPECIFIED
C310400 GLYCOGENOSIS WITH HEPATIC CIRRHOSIS
J61..00 CIRRHOSIS AND CHRONIC LIVER DISEASE
J610.00 ALCOHOLIC FATTY LIVER
J612.00 ALCOHOLIC CIRRHOSIS OF LIVER
J612.11 FLORID CIRRHOSIS
J612.12 LAENNEC'S CIRRHOSIS
J612000 ALCOHOLIC FIBROSIS AND SCLEROSIS OF LIVER
J613.00 ALCOHOLIC LIVER DAMAGE UNSPECIFIED
J613000 ALCOHOLIC HEPATIC FAILURE
J614.00 CHRONIC HEPATITIS
J614000 CHRONIC PERSISTENT HEPATITIS
J614100 CHRONIC ACTIVE HEPATITIS
J614111 AUTOIMMUNE CHRONIC ACTIVE HEPATITIS
J614200 CHRONIC AGGRESSIVE HEPATITIS
J614300 RECURRENT HEPATITIS
J614400 CHRONIC LOBULAR HEPATITIS
J614y00 CHRONIC HEPATITIS UNSPECIFIED
J614z00 CHRONIC HEPATITIS NOS
J615.00 CIRRHOSIS - NON ALCOHOLIC
J615.11 PORTAL CIRRHOSIS
J615000 UNILOBULAR PORTAL CIRRHOSIS
J615100 MULTILOBULAR PORTAL CIRRHOSIS
J615111 POSTNECROTIC CIRRHOSIS OF LIVER
J615200 MIXED PORTAL CIRRHOSIS
J615300 DIFFUSE NODULAR CIRRHOSIS
J615400 FATTY PORTAL CIRRHOSIS
J615500 HYPERTROPHIC PORTAL CIRRHOSIS
J615600 CAPSULAR PORTAL CIRRHOSIS
J615700 CARDIAC PORTAL CIRRHOSIS
J615711 CONGESTIVE CIRRHOSIS
J615800 JUVENILE PORTAL CIRRHOSIS
J615811 CHILDHOOD FUNCTION CIRRHOSIS
J615812 INDIAN CHILDHOOD CIRRHOSIS
J615900 PIGMENTARY PORTAL CIRRHOSIS
J615A00 PIPE-STEM PORTAL CIRRHOSIS
J615B00 TOXIC PORTAL CIRRHOSIS
J615C00 XANTHOMATOUS PORTAL CIRRHOSIS
J615D00 BACTERIAL PORTAL CIRRHOSIS
J615E00 CARDITUBERCULOUS CIRRHOSIS
J615F00 SYPHILITIC PORTAL CIRRHOSIS
J615G00 ZOOPARASITIC PORTAL CIRRHOSIS
J615H00 INFECTIOUS CIRRHOSIS NOS
J615y00 PORTAL CIRRHOSIS UNSPECIFIED
J615z00 NON-ALCOHOLIC CIRRHOSIS NOS
J615z11 MACRONODULAR CIRRHOSIS OF LIVER
J615z12 CRYPTOGENIC CIRRHOSIS OF LIVER
J615z13 CIRRHOSIS OF LIVER NOS
J615z14 LAENNEC'S CIRRHOSIS, NON-ALCOHOLIC
J615z15 HEPATIC FIBROSIS
J616.00 BILIARY CIRRHOSIS

J616000 PRIMARY BILIARY CIRRHOSIS
 J616100 SECONDARY BILIARY CIRRHOSIS
 J616200 BILIARY CIRRHOSIS OF CHILDREN
 J616z00 BILIARY CIRRHOSIS NOS
 J617000 CHRONIC ALCOHOLIC HEPATITIS
 J61y.00 OTHER NON-ALCOHOLIC CHRONIC LIVER DISEASE
 J61y000 CHRONIC YELLOW LIVER ATROPHY
 J61y100 NON-ALCOHOLIC FATTY LIVER
 J61y700 STEATOSIS OF LIVER
 J61yz00 OTHER NON-ALCOHOLIC CHRONIC LIVER DISEASE NOS
 J61z.00 CHRONIC LIVER DISEASE NOS
 J62..00 LIVER ABSCESS AND SEQUELAE OF CHRONIC LIVER DISEASE
 J625.00 [X] HEPATIC FAILURE
 J625.11 [X] LIVER FAILURE
 J62y.00 OTHER SEQUELAE OF CHRONIC LIVER DISEASE
 J62y.11 HEPATIC FAILURE NOS
 J62y.12 LIVER FAILURE NOS
 J62y.13 HEPATIC FAILURE
 J62z.00 LIVER ABSCESS AND CHRONIC LIVER DISEASE CAUSING SEQUELAE NOS
 J635300 TOXIC LIVER DISEASE WITH CHRONIC PERSISTENT HEPATITIS
 J635400 TOXIC LIVER DISEASE WITH CHRONIC LOBULAR HEPATITIS
 J635500 TOXIC LIVER DISEASE WITH CHRONIC ACTIVE HEPATITIS
 J635600 TOXIC LIVER DISEASE WITH FIBROSIS AND CIRRHOSIS OF LIVER
 SP14200 HEPATIC FAILURE AS A COMPLICATION OF CARE
 SP14211 LIVER FAILURE AS A COMPLICATION OF CARE

Venous Thromboembolism (both deep venous thrombosis and pulmonary embolism)

G801.11 Deep vein thrombosis
 G801.12 Deep vein thrombosis, leg
 G801.13 DVT - Deep vein thrombosis
 G822.00 Embolism and thrombosis of the vena cava
 G80y.11 Phlebitis and/or thrombophlebitis of iliac vein
 G80y200 Phlebitis of the external iliac vein
 G80y400 Thrombophlebitis of the common iliac vein
 G80y600 Thrombophlebitis of the external iliac vein
 G80y800 Phlebitis and thrombophlebitis of the iliac vein
 G801.00 Deep vein phlebitis and thrombophlebitis of the leg
 G801000 Phlebitis of the femoral vein
 G801100 Phlebitis of the popliteal vein
 G801200 Phlebitis of the anterior tibial vein
 G801400 Phlebitis of the posterior tibial vein
 G801500 Deep vein phlebitis of the leg unspecified
 G801600 Thrombophlebitis of the femoral vein
 G801700 Thrombophlebitis of the popliteal vein
 G801A00 Thrombophlebitis of the posterior tibial vein
 G801B00 Deep vein thrombophlebitis of the leg unspecified
 G801z00 Deep vein phlebitis and thrombophlebitis of the leg NOS
 G401.00 Pulmonary embolism
 G401.12 Pulmonary embolus

Oral Hypoglycemic Agents

ORAL ANTIDIABETICS_sulfonylureas

2108 Acetohexamide
2110 Tolazamide
2115 Tolbutamide
2116 Glibenclamide (aka Glyburide)
2133 Glibornuride
2139 Glipizide
2148 Gliclazide
2159 Glimepiride
2140 Gliquidone
2120 Chlorpropamide

ORAL ANTIDIABETICS_Acarbose

2157 Acarbose

ORAL ANTIDIABETICS_Biguanides

2122 Metformin

ORAL ANTIDIABETICS_Glinides

2161 Repaglinide
2165 Nateglinide

Dipeptidyl peptidase 4 inhibitors

1079 SITAGLIPTIN

Oral Antidiabetics_PPAR agonists

2163 ROSIGLITAZONE
2167 ROSIGLITAZONE AND METFORMIN
2160 TROGLITAZONE
2162 PIOGLITAZONE
51050 ROSIGLITAZONE + GLIMEPIRIDE
51067 PIOGLITAZONE / METFORMIN

Insulin

2103 INSULIN
2109 (CZI CRYSTALLIN ZINC INSULIN
2111 INSULIN ZINC SUSPENSION
2112 INSULIN ZINC SUSPENSION EXTENDED
2125 DEPOT-INSULIN CS
2128 GLOBIN ZINC INSULIN INJECTION
2129 KOMB-INSULIN
2136 INSULIN NOVO-RAPITARD
2138 INSULIN LEO
2141 LONG INSULIN
2144 INSULIN CS

2151 INSULIN HUM NPH W ISOPHANE
 2154 INSULIN HUM NPH W NEUTRAL/SOLUBLE

 2158 PRO-HUMAN INSULIN LISPRO
 16221 INSULINS & ORAL ANTIDIABETIC AGENTS
 51007 INSULIN PORC ZINK / LENTE SEMILENTE
 51008 INSULIN BEEF
 02170 HUMALOG

Statins

1214 PRAVASTATIN
 1217 FLUVASTATIN
 1218 ATORVASTATIN
 1219 CERIVASTATIN
 1220 SIMVASTATIN
 1221 ROSUVASTATIN CALCIUM
 1222 EZETIMIBE + SIMVASTATIN
 19103 SIMVASTATIN
 1212 LOVASTATIN

Antihypertensive Agents

ACE-inhibitors_P

2202 IMIDAPRIL HCL
 4555 CAPTOPRIL
 4559 ENALAPRIL
 4566 LISINOPRIL
 4574 PERINDOPRIL
 4575 RAMIPRIL
 4578 CILAZAPRIL
 4580 FOSINOPRIL
 4592 MOEXIPRIL
 4609 TRANDOLAPRIL
 5776 QUINAPRIL
 4584 Benazepril

ACE-inhibitor combinations

4618 PERINDOPRIL + INDAPAMIDE

ACE-inhibitors and diuretics

4569 CAPTOPRIL W HYDROCHLORTH
 4577 LISINOPRIL W HYDROCHLORO
 4581 ENALAPRIL W HYDROCHLOROT
 4590 benazepril hydrochlorothiazide

ACE-inhibitors and calcium channel blockers

4598 FELODIPINE+RAMIPRIL

Angiotensin II antagonists

4589 LOSARTAN
 4596 VALSARTAN
 4615 TELMISARTAN
 4617 EPROSARTAN
 6202 AMIAS (=Candesartan)
 6203 APROVEL (= Irbesartan)
 24518 OLMESARTAN MEDOXOMIL

Angiotensin II inhibitors and diuretics

4595 COZAAR-COMP
 6207 IRBESARTAN+HYDROCHLOROTH

Beta-blockers incl. Combination with diuretics

1320 ACEBUTOLOL HCL
 1321 TIMOLOL MALEATE
 1326 ATENOLOL
 4561 ATENOLOL W CHLORTHALIDON
 4562 NADOLOL W BENDROFLUMETHI
 4568 ATENOLOL W NIFEDIPINE
 4583 CELIPROLOL
 4611 NEBIVOLOL
 5710 PROPRANOLOL
 5723 OXPRENOLOL HCL
 5732 PINDOLOL
 5754 NADOLOL
 5757 CLOPAMIDE W PINDOLOL
 5769 BETAXOLOL
 5770 TIMOLOL,AMILORIDE,HYDROC
 5773 OXPRENOLOL W CYCLOPENTHI
 5778 ESMOLOL
 6140 METOPROLOL
 6178 PROPRANOLOL W BENDROFLUA
 6180 METOPROLOL W HYDROCHLORO
 6182 METOPROLOL W CHLORTHALID
 6184 SOTALOL W HYDROCHLOROTHI
 6185 TIMOLOL W BENDROFLUAZIDE
 6188 BISOPROLOL FUMARATE
 6191 CARTEOLOL HCL TABLETS
 6196 BISOPROLOLFUMARATE W HYD
 6798 AMILORIDE,ATENOLOL,HYDRO
 16704 FUROSEMIDE W PENBUTOLOL
 6164 LABETALOL HCL
 6166 SOTALOL HCL
 6198 CARVEDILOL
 6797 HYDROCHLOROTHIAZIDE W AC
 4594 TENBEN
 4599 HYDROCHLOROTHIAZIDE+TIMO
 5731 alprenolol
 6160 bupranolol hcl

1327 penbutolol
16704 furosemide w penbutolol

Calcium channel blockers

4579 FELODIPINE SR
4587 LACIDIPINE
4591 DILTIAEM + HYDROCHLOROT
4597 NISOLDIPINE
4598 FELODIPINE+RAMIPRIL
4607 ISRADIPINE
5733 VERAPAMIL
5779 VERAPAMIL HCL 180MG/2MG
6136 AMLODIPINE
6145 NIFEDIPINE
6148 PERHEXILINE MALEATE
6156 LIDOFLAZINE
6175 DILTIAZEM
6189 NIMODIPINE
6187 NICARDIPINE
6204 ZANIDIP
6205 MIBEFRADIL

Diuretics

Thiazides

6716 Bendrofluzide
4527 Benzthiazide
6746 Chlorothiazide
6734 Hydrochlorothiazide
4524 Cyclopenthiazide
6737 Polythiazide
6742 Chlorthalidone (thiazide-like)
6574 Mefruside (thiazide-like)
6770 Xipamide (thiazide-like)
6758 Metolazone
6748 Hydroflumethiazide
6764 Clopamide
16703 Clopamide with potassium
4554 Indapamide

Loop diuretics

6718 Furosemide
6756 Bumetanide
16711 Torasemide
6720 Ethacrynic acid

Kalium-sparing diuretics

6719 Triamterene
6753 Amiloride
6701 Spironolactone
6420 Metyrapone

Diuretics/combinations

6702 Acetazolamide
 16710 Bumetanide + amiloride
 6794 Furosemide + amiloride
 6795 Furosemide + triamterene
 6785 Chlorthalidone + triamterene
 6721 Hydrochlorothiazide + triamterene
 6796 Furosemide + spironolactone
 6717 SPIRONOLACTONE W HYDROCHLOROTHIAZIDE
 6763 Spironolactone + thiazides
 6750 Amiloride + hydrochlorothiazide
 4576 Amiloride + cyclopenthiiazide

Thiazides with antihypertensives

4561 ATENOLOL W CHLORTHALIDONE
 6798 AMILORIDE,ATENOLOL,HYDROCHLOROTHIAZIDE

4594 Atenolol
 6797 Acebutolol
 6196 Bisoprolol
 4562 Nadolol
 5773 Oxprenolol
 5757 Pindolol
 5770 TIMOLOL,AMILORIDE,HYDROCHLORTHIAZIDE
 6185 Timolol
 4556 PROPRANOLOL W HYDROCHLORTHIAZIDE
 6178 Propranolol
 6180 METOPROLOL W HYDROCHLOROTHIAZIDE
 6182 Metoprolol
 6184 Sotalol
 4569 Captopril
 4581 Enalapril
 4608 Quinapril
 4577 Lisinopril
 4591 Diltiazem
 4515 RESERPINE W HYDROCHLOROTHIAZIDE PLUS
 4525 CYCLOPENTHIAZIDE W POTASSIUM CHLORIDE
 4517 METHYLCLOTHIAZIDE W DESERPIDINE
 4530 CYCLOPENTHIAZIDE,RESERPINE,POTASSIUM CHLORIDE
 4532 GUANETHIDINE,CYCLOPENTHIAZIDE,POTASSIUM CHLORIDE
 4536 HYDROFLUMETHIAZIDE,KCL,RAUWOLFIA,SERPENTHE
 4539 GUANETHIDINE W HYDROCHLOROTHIAZIDE
 4544 BUTABARBITAL,HYDROCHLOROTHIAZIDE,RESERPINE
 4552 CLONIDINE W CHLORTHIAZIDE
 4557 HYDRALAZINE W HYDROCHLOROTHIAZIDE
 4564 METHOSERPIDINE W BENZTHIAZIDE
 4582 LISINOPRIL W HYDROCHLOROTHIAZIDE
 4585 ALKAVERVIR W EPITHIAZIDE
 4590 BENAZEPRIL, HYDROCHLOROTHIAZIDE
 4599 HYDROCHLOROTHIAZIDE+TIMOLOL+AMILORIDE

4601 METHYLDOPA W HYDROCHLOROTHIAZIDE
4602 (METHYLCLOTHIAZIDE W DESERPINE
4603 METHYLDOPA W CHLOROTHIAZIDE
6146 RESERPIN,DIHYDRALAZINE,HYDROCHLOROTHIAZIDE,KCL
6207 IRBESARTAN+HYDROCHLOROTHIAZIDE
6707 HYDROCHLOROTHIAZIDE W POTASSIUM CHLORIDE
6711 BENDROFLUMETHIAZIDE W POTASSIUM CHLORIDE
6723 METHYLCLOTHIAZIDE
6728 BENDROFLUMETHIAZIDE,RAUWOLFIA SERP,KCL
6735 TRICHLORMETHIAZIDE
6736 HYDROCHLOROTHIAZIDE W MEPROBAMATE
6738 TRICHLOMETHIAZIDE W RESERPINE
6739 CHLOROTHIAZIDE W RESERPINE
6741 (GUANETHIDINE W HYDROCHLOROTHIAZIDE
6744 CYCLOTHIAZIDE W POTASSIUM CHLORIDE
6749 CYCLOTHIAZIDE
6750 HYDROCHLOROTHIAZIDE W AMILORIDE HCL
6762 POLYTHIAZIDE W RESERPINE
6771 BUTHIAZIDE
6783 (SPIRONOLACTONE W HYDROCHLOROTHIAZID
6789 TRIAMTERINE W BENZTHIAZIDE
6792 (AMILORIDE W HYDROCHLOROTHIAZIDE
9001 CRYPTENAMINE W METHYLCLOTHIAZIDE
16701 CHLOROTHIAZIDE W SPIRONOLACTONE
16702 CHLOROTHIAZIDE W SPIRONOLACTONE,LACTOSE
16709 ETHIAZIDE
40007 HYDROCHLOROTHIAZIDE OR PLACEBO STUDY
6731 QUINETHAZONE
4545 DIHYDROERG,CLOPAMIDE,RESERPINE
5758 PINDOLOL W CLOPAMIDE
6742 CHLORTHALIDONE
6782 CHLORTHALIDONE/POT.CHLORIDE
6150 RESERPIN,MEFRUSID,INOSITONICOT
4618 PERINDOPRIL + INDAPAMIDE
6752 CLOREXOLONE
6733 MERSALYL SODIUM
9198 PHENOBARBITAL W THEOBROMINE
4551 RESERPINE W FUROSEMIDE
6768 FUROSEMIDE W POTASSIUM
6793 (FUROSEMIDE W POTASSIUM
16704 FUROSEMIDE W PENBUTOLOL
6759 BUMETANIDE W POTASSIUM CHLORIDE
4605 PIRETANIDE
6790 TIENILIC ACID
6784 ETHACRYNIC ACID W TRASICOR
6766 ETOZOLIN
6781 LASIX W SPIRONOLACTON
6783 (SPIRONOLACTONE W HYDROCHLOROTHIAZID
6786 SPIRONOLACTONE W COMBINATIONS
16701 CHLOROTHIAZIDE W SPIRONOLACTONE
16702 CHLOROTHIAZIDE W SPIRONOLACTONE,LACTOSE

16708 POTASSIUM CANRENOATE
16712 EPLERENONE
4599 HYDROCHLOROTHIAZIDE+TIMOLOL+AMILORIDE
4616 TRIAMTERINE+AMILORIDE
16710 BUMETANIDE W AMILORIDE
4616 TRIAMTERINE+AMILORIDE
6765 BEMETIZIDE W TRIAMTERENE
6789 TRIAMTERINE W BENZTHIAZIDE

Nitrates

B06106 NITROGLYCERINE EXT.RELEASE
B06127 NITROGLYCERIN
B06167 NITROGLYCERIN + ISOSORBIDEDNITRAT
B06171 NITROGLYCERIN W COMBINATIONS
B06174 NITROGLYCERINE DISC
B06176 ISOSORBIDE MONONITRATE
B06206 ISOSORBIDE MONONITRATE+ASPIRIN
B06128 ISOSORBIDE DINITRATE
B06141 SODIUM NITROPRUSSIDE
B06153 AMYL NITRITE

Antiplatelet Agents

1923 EPOPROSTENOL
1928 ABCIXIMAB
1930 CLOPIDOGREL
5528 TICLOPIDIN
6105 DIPYRIDAMOLE
6201 DIPYRIDAMOLE 200MG/ASPIR
4979 Aloxiprin
1937 Tirofiban

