3.4 Endpoints

All codes relevant to abstracting diagnostic, drug, and laboratory data appear in Appendix 1.

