3.4.2 Off-label use

These outcomes will be ascertained using AUPD or the Danish National Registry of Patients in Denmark and using the GPRD's Event File or Drug File in the UK. Off-label use will be defined as prescription of rosiglitazone dispensed by/issued to:

- Patients aged 16 years or younger at the time of any rosiglitazone prescription;
- Patient with concomitant use of insulin, defined as at least one prescription for insulin in between the first and last prescription for rosiglitazone²;
- Patients diagnosed with type 1 diabetes mellitus;

- Women with gestational diabetes without evidence of pre-gestational diabetes (UK only);
- Women with polycystic ovary syndrome (UK only)

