3.5 Covariates definition and measurement

Baseline comorbidities will be ascertained by examining inpatient and outpatient hospital diagnoses in the ten years preceding study enrolment and recorded in the Danish National Registry of Patients in Denmark and in the GPRD's Event File in the UK. We will use the Charlson comorbidity index to summarise comorbidities (other than diabetes) in the analysis.¹⁹

Use of prescription medication other than oral glucose lowering therapy will be ascertained based on prescription history (AUPD in Denmark; Drug File in the GPRD). Concomitant use will be defined as a record of at least one prescription for a medication that falls in one of the categories listed below between the first and the last prescription for glucose lowering therapy.

- Lipid-lowering agents (statins);

- Antihypertensive agents (ACE inhibitors, angiotensin receptor blockers, beta-blockers, calcium-channel blockers);
- Diuretics (loop, potassium sparing, thiazide);
- Nitrates;
- Antiplatelet agents.

Smoking, alcoholism, and body mass index (BMI) are available for about 70% of the patients in the GPRD's Additional Clinical Detail File (for the UK). In Denmark, these data are not generally recorded in registries, although there are diagnostic codes for obesity and alcoholism, which we will use to identify patients who were hospitalised. It may be possible to obtain data on smoking, body mass index and blood pressure at least on some members of the study population via linkage to the National Indicator Project and Danish Registry of Patients. The size of subgroup with available data on smoking, alcoholism, and BMI will not be known until data linkage.

Age and sex of the patients: in Denmark, date of birth and sex are encoded in the unique identifier that will be used to link the data; in the UK, the GPRD records the demographic data in the Registration File.

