Appendix 1. Codes used in data abstraction

Diagnostic codes used to Abstract the Danish National Registry of Patients and the Registry of Causes of Death

Disease/condition	ICD-8 code	ICD-10 code
Diabetes type 1	249.00; 249.06; 249.07; 249.09	E10.0, E10.1; E10.9
Diabetes type 2	250.00; 250.06; 250.07; 250.09	E11.0; E11.1; E11.9
Acute myocardial infarction	410	I21, I22, I23
Ischemic heart disease (acute and chronic)	411-414	I20, I24, I25
Congestive heart failure	427.09, 427.10, 427.11, 427.19, 428.99, 782.49;	I50, I11.0, I13.0, I13.2
Other cardiac disease	393–398, 400–404	I05–I09
Peripheral vascular disease	440, 441, 442, 443, 444, 445	I70, I71, I72, I73, I74, I77
Ischemic stroke	430-438 (cerebrovascular disease)	I63-64
Alcoholism	291, 303, 577.10, 571.09, 571.10	F10.1-F10.9, G31.2, G62.1, G72.1, I42.6, K29.2, K86.0, Z72.1
Obesity	277.99	E65-E66
Mild liver disease	571, 573.01, 573.04	B18, K70.0–K70.3, K70.9, K71, K73, K74, K76.0
Moderate to severe liver disease	070.00, 070.02, 070.04, 070.06, 070.08, 573.00, 456.00–456.09	B15.0, B16.0, B16.2, B19.0, K70.4, K72, K76.6, I85
Deep vein thrombosis	451.00	I81, I82
Pulmonary embolism	450.99	I26

ICD-8: http://www.sst.dk/Indberetning%20og%20statistik/Klassifikationer/SKS_download.aspx

ICD-10: <http://apps.who.int/classifications/apps/icd/icd10online/>

Diagnostic codes used to compute Charlson Comorbidity Index¹⁹

Disease	ICD-8 code	ICD-10 code
Myocardial infarction	410	I21;I22;I23
Congestive heart failure	427.09; 427.10; 427.11; 427.19; 428.99; 782.49	I50; I11.0; I13.0; I13.2
Peripheral vascular disease	440; 441; 442; 443; 444; 445	I70; I71; I72; I73; I74; I77
Cerebrovascular disease	430-438	I60-I69; G45; G46
Dementia	290.09-290.19; 293.09	F00-F03; F05.1; G30
Chronic pulmonary disease	490-493; 515-518	J40-J47; J60-J67; J68.4; J70.1; J70.3; J84.1; J92.0; J96.1; J98.2; J98.3
Connective tissue disease	712; 716; 734; 446; 135.99	M05; M06; M08; M09;M30;M31; M32; M33; M34; M35; M36; D86
Ulcer disease	530.91; 530.98; 531-534	K22.1; K25-K28
Mild liver disease	571; 573.01; 573.04	B18; K70.0-K70.3; K70.9; K71; K73; K74; K76.0
Diabetes type1	249.00; 249.06; 249.07; 249.09	E10.0, E10.1; E10.9
Diabetes type2	250.00; 250.06; 250.07; 250.09	E11.0; E11.1; E11.9
Hemiplegia	344	G81; G82
Moderate to severe renal disease	403; 404; 580-583; 584; 590.09; 593.19; 753.10- 753.19; 792	I12; I13; N00-N05; N07; N11; N14; N17-N19; Q61
Diabetes with end organ damage type1	249.01-249.05; 249.08	E10.2-E10.8

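### The Danish type 1 diabetes code row leaves out the type 1 codes with end-organ damage, so the Danish type 1 off-label category can only be undercounted

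*Protocol*

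**What the plan says.** Protocol section 3.4.2 lists among the off-label groups "Patients diagnosed with type 1 diabetes mellitus". The item is not limited to uncomplicated disease and, unlike the last two items in that list, is not restricted to the UK. On the Danish source the section says: "These outcomes will be ascertained using AUPD or the Danish National Registry of Patients in Denmark".

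Section 3.4 makes the appendix the governing code list: "All codes relevant to abstracting diagnostic, drug, and laboratory data appear in Appendix 1".

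In Appendix 1, the table for abstracting the Danish National Registry of Patients and the Registry of Causes of Death has one type 1 row. It holds ICD-8 "249.00; 249.06; 249.07; 249.09" and ICD-10 "E10.0, E10.1; E10.9".

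A second table, headed as serving the Charlson index, repeats that row and adds another labelled "Diabetes with end organ damage type1". The added row holds ICD-8 "249.01-249.05; 249.08" and ICD-10 E10.2 to E10.8.

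On the use of the Charlson index, section 3.5 says: "We will use the Charlson comorbidity index to summarise comorbidities (other than diabetes) in the analysis".

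**The concern.** The outcome in section 3.4.2 is any type 1 diagnosis, but the row that would find it covers only the type 1 codes outside the end-organ-damage group. The appendix itself recognises the other codes as type 1, and prints them where they serve a different purpose. That purpose then excludes diabetes, so the codes have no stated use in the analysis.

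Off-label use is one of the protocol's specific aims, and section 3.6.2 reports off-label proportions for each country and over time. A gap in the Danish code list therefore feeds straight into a reported Danish figure. The people it can miss are type 1 patients with recorded organ damage.

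**Working it through.** The plan states no figure for this outcome, so there is nothing to reproduce. The check compares the two Appendix 1 rows as sets and then sets out how a missed code becomes a missed patient.

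**Step 1: ICD-10.** The two type 1 rows together name E10.0 to E10.9, which is 10 codes.
- Abstraction row: E10.0, E10.1, E10.9 = 3 codes.
- 10 − 3 = 7 codes left: E10.2 to E10.8.
- Charlson end-organ row: E10.2 to E10.8 = 7 codes. It is identical to the remainder and does not overlap the abstraction row.

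**Step 2: ICD-8.** The two rows together name 249.00 to 249.09, which is 10 codes.
- Abstraction row: 249.00, 249.06, 249.07, 249.09 = 4 codes.
- 10 − 4 = 6 codes left: 249.01 to 249.05 and 249.08.
- Charlson end-organ row: the same 6 codes, again with no overlap.

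The abstraction row is thus exactly the Charlson row for type 1 without organ damage, down to the mixed comma and semicolon in the ICD-10 cell. This looks like one of two rows carried over, and no text gives a reason for a narrower definition. By contrast, the UK diabetes list, which covers non-specific and type II disease, includes renal, ophthalmic, neurological and other complication codes.

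**Step 3: which code set matters when.** Section 6.1 says the registry has used ICD-10 since 1994 and ICD-8 before that. The study period starts in 2000, so diagnoses made during it depend on the E10 part. The 249 part matters for history recorded before 1994.

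**Step 4: from codes to patients.** Let T be the Danish rosiglitazone users with any type 1 code, s the share of T who carry only end-organ codes, and i the share of those who meet another off-label criterion.
- Type 1 category as coded: T × (1 − s).
- Missed in the type 1 category: T × s.
- Missed from total off-label use: T × s × (1 − i).

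All three factors are zero or positive, so the error has one direction. The documents give none of T, s or i. For scale only, under assumed values of s:

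| Assumed s | Share of type 1 users captured (1 − s) |
|---|---|
| 0% | 100% |
| 10% | 90% |
| 25% | 75% |
| 50% | 50% |

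**Step 5: after the change.** With the union of the two rows, coverage goes from 3 to 10 of 10 ICD-10 codes and from 4 to 10 of 10 ICD-8 codes, and s no longer matters.

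**Step 6: type 2.** The type 2 abstraction row has the same pattern: E11.2 to E11.8 and 250.01 to 250.05 with 250.08 appear only in the Charlson table.

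**The case against.** **The codes are already in Appendix 1, labelled type 1.** Section 3.4 points to the whole appendix. Since diabetes is taken out of the Charlson summary, the diabetes rows there might be meant to identify diabetes type as well. No text supports this. The table is headed for the Charlson index, and the abstraction table has its own type 1 row. A programmer following the document would use that row.

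**Missed patients may still be off-label.** This stands. Section 3.4.2 also counts anyone with at least one insulin prescription between the first and last rosiglitazone prescriptions, and the Danish insulin codes are listed. A reader might infer that every complication-only type 1 patient is classed as on-label. The documents do not support that: the certain effect is on the type 1 category, and total off-label use is affected only for those who meet no other criterion.

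**Counting codes is not counting patients.** This also stands. A reader might infer from 7 of 10 and 6 of 10 missing codes that most type 1 patients are lost. One contact with E10.0, E10.1 or E10.9 is enough for capture, and section 6.1 describes up to 20 diagnoses per contact, with hospitalisations since 1977 and outpatient visits since 1995. The share with complication codes only may be small.

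**Type 2.** A reader might infer that the type 2 gap drops complicated type 2 patients from the Danish cohort. Section 3.3 identifies patients by two or more prescriptions for oral glucose-lowering drugs, and no section requires a type 2 diagnosis code for entry. That inference fails.

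**Conclusion.** The point holds for the Danish type 1 off-label category. The abstraction row omits every code that the appendix labels type 1 with end-organ damage, in both ICD versions, while section 3.4.2 counts any type 1 diagnosis. Applied as written, the code list can only lower the Danish type 1 count.

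The size is unknown. It depends on how many Danish users (about 2,400 rosiglitazone users in the prescription database) have type 1 codes, and on how many of those have complication codes only. The documents give neither, so any patient count would rest wholly on assumption. The effect on total off-label use is no larger than the effect on the type 1 category, and is smaller to the extent that the insulin criterion or another criterion catches the same people.

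The point concerns one descriptive outcome in the smaller of the two data sources. Nothing in the protocol shows the risk ratios, laboratory comparisons or utilisation trends to depend on it. It is worth correcting because the direction is certain and the remedy is simple.

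**What to change.** In the Danish abstraction table of Appendix 1, define type 1 diabetes as E10.0-E10.9 and 249.00-249.09. This is the union of the two type 1 rows already printed. For consistency, define type 2 diabetes as E11.0-E11.9 and 250.00-250.09, again the union of printed rows. The type 2 change tidies the code list and should not be presented as recovering patients for the prescription-defined cohort.

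The Charlson table can stay as it is.

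The cost is a code-list edit with no new data source. The protocol mentions only preliminary linkage and does not say whether diagnoses have been extracted. If they have been, using the narrow row, the diabetes query would need to be rerun.
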